#### 9 CONTENT OF REPORTS

## 9.1 Within-Trial Analyses Performed To Date

Not applicable.

#### 10 CONVENTIONS

The following conventions may be used for imputing partial dates for analyses requiring dates:

- For missing and partial adverse event onset dates, imputation will be performed using the Adverse Event Domain Requirements Specification .
- Missing and partial Non-Study Medication Domain dates will be imputed using the derivation algorithm described in 4.3.3 of BMS Non-Study Medication Domain Requirements Specification 18.
- Missing and partial radiotherapy and surgery dates will be imputed using algorithm described in APPENDIX 2.

For death dates, the following conventions will be used for imputing partial dates:

- If only the day of the month is missing, the 1st of the month will be used to replace the missing day. The imputed date will be compared to the last known date alive and the maximum will be considered as the death date.
- If the month or the year is missing, the death date will be imputed as the last known date alive.
- If the date is completely missing but the reason for death is present the death date will be imputed as the last known date alive

For date of progression, the following conventions will be used for imputing partial dates:

- If only the day of the month is missing, the 1st of the month will be used to replace the missing day.
- If the day and month are missing or a date is completely missing, it will be considered as missing.
- In case of the date of death is present and complete, the imputed progression date will be compared to the date of death. The minimum of the imputed progression date and date of death will be considered as the date of progression.

For other partial/missing dates, the following conventions may be used:

- If only the day of the month is missing, the 15th of the month will be used to replace the missing day.
- If both the day and the month are missing, "July 1" will be used to replace the missing information.
- If a date is completely missing, it will be considered as missing.

The following conversion factors will be used to convert days to months or years:

1 month = 30.4375 days and 1 year = 365.25 days.

Duration (e.g. DOR, etc) will be calculated as follows:

Duration = (Last date - first date + 1)

All statistical analyses will be carried out using SAS (Statistical Analysis System software, SAS Institute, North Carolina, USA) unless otherwise noted.

#### 11 CONTENT OF REPORTS

All analyses describe in this SAP will be included in the Clinical Study Report except where otherwise noted. Refer to the Data Presentation Plan for mock-ups of all tables and listings.

#### 12 DOCUMENT HISTORY

#### **Document History**

Document History				
Version Number	Author(s)	Description		
1.0		Initial version dated 18-Oct-2017		
2.0		Version 2.0 dated 28-Aug-2020		
		
 
Updated the definition for the outcome research exploratory endpoint FACT-E and added the analysis window for outcome research assessments in Section 4.3.3.
 
		
		
 
Added Max-Combo method as a sensitivity analysis accounting for the potential non-proportionality observed from the OS/PFS KM curves in Section 7.5.2.2.
 
		
		
 
Added PFS2/TSST as an exploratory endpoint (Section 4.3.1) and the corresponding analysis (Section 7.5.4.2).
 
		
		• Removed the procedures for the reinitiation of nivolumab ± ipilimumab treatment after disease progression for up to 1 additional year.		
		
 
Modified the Safety section (Section 7.6) to incorporate the contents from the safety section in the IO CORE SAP.
 
		
		
 
Added value "Gx" for histologic grade at initial diagnosis and added prior surgery and prior radiotherapy in Section 7.5.2.3.
 
		
		
 
Added 5% and 10% as additional subgroups for PD-L1 status in Section 7.8.1.2.
 
		
		
 
Added analysis to explore the association between ORR and PD-L1 in Section 7.8.1.2.
 
		
		
 
Added some additional analyses for EQ-5D-3L and FACT-E in Section 7.9.
 
		
		
 
Added APPENDIX 5 with analyses of data from China.
 
		
		
 
Added the imputation algorithm for missing and partial radiotherapy and surgery dates from IO CORE SAP (APPENDIX 2).
 
		
3.0		Version 3.0 dated 29-Oct-2020		
		
 
Added language and rationale to allow for the final PFS analysis to be triggered when 136 PFS events per BICR are observed among the PD-L1 expressing subjects in the chemotherapy arm or when at least 12 months minimum follow up is reached, if the target number of PFS events is unlikely to be reached in Section 1, Section 5 and APPENDIX 7.
 
		

#### **Document History**

Version Number	Author(s)		Description
4.0		Version 4.0 dated Feb 12, 2021	

#### Main changes include

- Added analysis to evaluate relevant treatment effect between N+I vs. N+C for key efficacy endpoints in Section 8.
- Added PD-L1 by CPS and MSI analysis in Section 7.8.2.
- Add language in section 7.1 to handle the small stratum in the stratified analyses.

#### Other minor changes include

- Aligned the PFS2/TSST definition with IO Core SAP in Section 4.3.1.
- Modified the baseline definition for stratification factors as before the date of the randomization in Section 6.1.
- Moved the definition of exploratory biomarker endpoints to Section 4.3.6.
- Added definition for All PD-L1 Negative Subjects and All Treated PD-L1 Expressing Subjects in Section 6.3.
- Added on-treatment curative Surgery as the relevant protocol deviation in Section 7.2.2.
- Add in Section 7.5.2.2 'The list of covariates considered in the multivariate cox model may be modified if there are issues with multicollinearity among the covariates or other important prognostic factors are identified.'
- Added limited safety analyses in PD-L1 expressing subjects and PD-L1 negative subjects in Section 7.6 to assess benefit-risk in PD-L1 subgroups.
- Aligned the baseline definition in Section 7.9 with Table 4.3.3-1.
- Added PRO analysis in All PD-L1 expressing subjects in addition to all treated subjects in Section 7.9.
- Added a stacked bar graph for GP5 in Section 7.9.
- Added COVID-19 Related Analysis in Section 7.10.
- Added Section 9.1 there was no within-trial analyses performed to date.
- Add definition of primary and secondary China subpopulation in APPENDIX 5. Includes 'Only unstratified analyses will be performed for efficacy endpoints and the sensitivity analysis of investigating nonproportionality in Kaplan-Meier curves will not be performed.' in APPENDIX 5.
- Removed metastatic disease from prior anti-cancer therapy in Section 7.3.4.
- Modified the subcategories for disease status at current diagnosis in the multivariate cox model in Section 7.5.2.2.
- In the Section 7.5.2.3 consistency of treatment effect in subsets, added region (Asia, non-Asia) and excluded biopsy from prior surgery.
- Removed safety summary in the 3 arms pooled (total) in Section 7.6 safety.
- For the odds ratio, in addition to 95% CI, also added '(in case the given endpoint is formally tested, also with the  $100(1-\alpha)\%$  CI)' in Section 7.5.3.2.
- In Section 7.3.2 demographics and other baseline characteristics, added race (Asia vs. non-Asia)

## **Document History**

Version Number	Author(s)	Description	
		• Modified the relative dose intensity formula for fluorouracil in Table 7.4.1-2	
		
 
The time to response would analyzed descriptively only for subjects who achieved PR or CR. KM estimate of time to response was removed.
 
	
		
 
Removed alpha adjusted difference in ORRs in Section 7.8.1.2 Association between PD-L1 status and efficacy
 
	
		
 
Add in Section 7.3.2 For the purposes of baseline characteristic summary, stratification factors will be retrieved from the CRF.
 
	
		
 
Remove alpha adjusted CI for ORR in Section 7.8.1.2 association between PD-L1 status and efficacy.
 
	

## APPENDIX 1 APPENDIX: EXAMPLE FOR SEQUENTIALLY REJECTIVE PROCEDURE

[figure not shown]
Section 7.5.1 of this SAP specifies the multiple testing procedure that controls family-wise Type I error rate of 5% in the strong sense across all primary and secondary endpoints. After rejecting an individual hypothesis, the local significance levels and the transition weights of the edges are updated: the rules for that update are determined by Algorithm 1 in Maurer and Bretz (2013). The resulting sequentially rejective testing procedure is uniquely determined by the graph in Figure 7.5.1-1. In order to illustrate the principles of this iterative procedure (summarized in Section 7.5.1), a simple hypothetical example is provided in this section.

This example considers a hypothetical outcome of the primary and secondary endpoints at the time of the PFS analysis (Time 1) and at the final OS analysis (Time 2). At Time 1, per protocol, all primary endpoints are formally tested (and thus all observed p-values are available): we assume that PFS in PDL1-expressing subjects is significant in the N+I vs. CT comparison at its initially allocated alpha. The 4 steps below demonstrate how the alpha will then be passed to the next testing based on the pre-specified testing strategy. At each step, a hypothesis is rejected (part A), its corresponding vertex and all edges will be removed; the remaining edges and nominal significance levels will be updated (part B). In the following, shaded vertices represent those hypotheses that are rejected at their nominal significance level at the given step. (For the sake of simplicity, examples of observed p-values are not provided.) (Notice the following: although the design assumes the same treatment effect and thus observed event numbers for the N+I vs. CT and N+C vs. CT comparisons, in the example, the OS information fractions observed at Time 1 are slightly different for the two comparisons. This reflects the fact that although the true treatment effect is assumed to be the same across comparisons, the observed number of events per comparison [N+I vs. CT and N+C vs. CT] is a random number.)

**Step 1**: At Time 1, reject primary endpoint PFS in PDL1-expressing subjects for N+I vs. CT (shaded vertex). As a result, the graph is updated as follows (see also Part B in table below):

- the rejected hypothesis and its outgoing edge is removed;
- the entire significance level of the rejected hypothesis is passed to the corresponding secondary endpoint in all randomized subjects (within the N+I vs. CT comparison).

Table 10-1: Step1: Time 1, Rejection of PFS PDL1+ for N+I vs. CT

[figure not shown]
\* Nominal signifiance levels for Time 1 / Time 2, based on O'Brien-Fleming with 72% observed information fraction at Time 1

\*\* Nominal signifiance levels for Time 1 / Time 2, based on O'Brien-Fleming with 68% observed information fraction at Time 1

**Step 2**: Now assume that the secondary endpoint PFS in all randomized subjects for N+I vs. CT (shaded vertex) is significant at Time 1 at its nominal alpha. As a result, the graph is updated as follows (see also Part B in table below):

- the rejected hypothesis and its outgoing edges are removed;
- half of the rejected hypothesis' significance level is passed to ORR in PDL1-expressing subjects (secondary endpoint) and thus it can be now tested at 0.0075;
- half of the rejected hypothesis' significance level is passed to another primary endpoint, OS in in PDL1-expressing subjects and thus latter's local significance level is updated from 0.01 to 0.0175. The alpha spending function (O'Brien-Fleming with 72% information fraction at Time 1) is then re-applied to this updated local significance level.

Table 10-2: Step2: Time 1, Rejection of PFS AC for N+I vs. CT

[figure not shown]
\* Nominal signifiance levels for Time 1 / Time 2, based on O'Brien-Fleming with 72% observed information fraction at Time 1

\*\* Nominal signifiance levels for Time 1 / Time 2, based on O'Brien-Fleming with 68% observed information fraction at Time 1

Step 3: For the sake of illustration, assume that no more endpoints can be rejected at Time 1, and thus the study continues to Time 2. As the PFS and ORR endpoints were not planned to be tested at Time 2, all related vertices and edges are removed from the graph. All OS endpoints will now use the nominal significance levels for Time 2, as determined by their alpha spending functions. Assume that we can reject primary endpoint OS in PDL1-expressing subjects for N+I vs. CT (shaded vertex) at its nominal significance level of 0.0162. As a result, the graph is updated as follows (see also Part B in the table below):

- the rejected hypothesis and its outgoing edge are removed;
- The entire local significance level of the rejected hypothesis is passed to its corresponding secondary endpoint in all randomized subjects in N+I vs. CT and thus the secondary endpoint's local significance level (across timepoints) is updated to 0.0175. The alpha spending function (Pocock with 65% information fraction at Time 1) is then applied to this updated alpha level, and it can be tested at 0.0078.

Table 10-3: Step3: Time 2, Rejection of OS PDL1+ for N+I vs. CT

\* Nominal signifiance levels for Time 1 / Time 2, based on O'Brien-Fleming with 72% observed information fraction at Time 1

\*\* Nominal signifiance levels for Time 1 / Time 2, based on O'Brien-Fleming with 68% observed information fraction at Time 1

\*\*\* Nominal signifiance levels for Time 1 / Time 2, based on Pocock with 65% observed information fraction at Time 1

Step 4: Reject OS in all randomized subjects for N+I vs. CT (shaded vertex) at Time 2. As a result:

- the rejected hypothesis and its related edges are removed;
- its entire significance level is passed to the last testable primary endpoint, OS in PDL1-expressing subjects for N+C vs. CT. Thus latter's local significance level is updated to 0.0275. The alpha spending function (O'Brien-Fleming with 68% information fraction at Time 1) is then applied to this updated alpha level, and it can be tested at 0.0257.

Table 10-4: Step4: Time 2, Rejection of OS AC for N+I vs. CT

Part A: Reject Hypothesis		Part B: Update Graph after Rejection	
N + I vs CT	N + C vs CT	N + I vs CT	N + C vs CT
0.0175 [0.0131/ 0.0078 **]	0.01 (0.0013 / 0.0096 °)  OS  PDL1  3  OS  AC		0.0275 [0.0056 / 0.0257 *]  OS  PDL1  AC

\* Nominal signifiance levels for Time 1 / Time 2, based on O'Brien-Fleming with 68% observed information fraction at Time 1

\*\* Nominal signifiance levels for Time 1 / Time 2, based on Pocock with 65% observed information fraction at Time 1 Assuming that OS in PDL1-expressing subjects for N+C vs. CT cannot be rejected, the process stops.

## APPENDIX 2 MISSING AND PARTIAL RADIOTHERAPY AND SURGERY DATES IMPUTATION ALGORITHMS

#### **Procedures – Imputation Rules.**

If reported procedure start date is a full valid date then set start date equal to the date part of procedure start date.

In case of partial date use imputation rules described below:

- If only day is missing then
  - If month and year of procedure match month and year of first dose date then impute as date of first dose;
  - If month and year of procedure don't match month and year of first dose date then impute as first day of that month and year.
- If both day and month are missing, then impute as maximum between 01JAN of the year and date of the first dose;
- If date is completely missing or invalid then leave missing.

Note: Imputation is not applicable to data where start date is not collected (for example "PRIOR RADIOTHERAPY" CRF). Set start date to missing in this case.

If reported end date is a full valid date then set end date equal to the date part of the reported end date.

In case of partial date use imputation rules described below:

- If reported end date is partial then set end date equal to the last possible reported end date based on the partial entered reported end date.
- If reported end date is missing, continuing, unknown or invalid then set end date equal to the most recent database extraction date.

If end date was imputed then compare end date to the death date or last known alive date if subject is not dead. If posterior then end date should be imputed to death date (or last known alive date if subject not dead).

Note: Imputation of partial dates only applies to data entered on "RADIOTHERAPY" CRF page. For other CRF pages in case of partial dates set end date to missing.

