# 4.1.2 Progression-Free Survival per BICR in All PD-L1 Expressing Subjects

For the purposes of the primary endpoints, PFS is as assessed by BICR in subjects with PD-L1 expressing tumors.

PFS is defined as the time from randomization to the date of the first documented PD per BICR or death due to any cause. Subjects without any baseline scan will be censored at the randomization date (regardless of death). Subjects who did not have any on-study tumor assessments and did not die (or died after initiation of the subsequent anti-cancer therapy) will be censored at the randomization date. Subjects who die without a reported prior PD per BICR (and die without start of subsequent therapy) will be considered to have progressed on the date of death. Subjects who did not have documented PD per BICR per RECIST1.1 criteria and who did not die, will be censored at the date of the last evaluable tumor assessment on or prior to initiation of the subsequent anti-cancer therapy. Subjects who started any subsequent anti-cancer therapy without a prior reported PD per BICR will be censored at the last tumor assessment on or prior to initiation of the subsequent anti-cancer therapy.

See Figure 4.1.2-1 for the graphical representation of this definition.

Figure 4.1.2-1: Graphical Representation of the Primary PFS Definition

rand = randomization, subs = subsequent therapy

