## 4.2.3 Objective Response Rate per BICR in All Randomized Subjects

Objective response rate as assessed by BICR in subjects with PD-L1 expressing tumors and in All Randomized subjects are secondary endpoints for this study.

It is defined as the number of subjects with a best overall response (BOR) of CR or PR divided by the number of randomized subjects in the population for each treatment group. BOR is defined as the best response designation as determined by BICR per RECIST 1.1, recorded between the date of randomization and the date of objectively documented progression or the date of subsequent anti-cancer therapy (including tumor-directed radiotherapy and tumor-directed surgery), whichever occurs first. For subjects without documented progression or subsequent anti-cancer therapy, all available response designations will contribute to the BOR determination. For subjects who continue treatment beyond progression, the BOR will be determined based on response designations recorded up to the time of the initial RECIST 1.1-defined progression.

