## 7.4.3.1 Subsequent Therapy

- Number and percentage of subjects receiving subsequent therapies will be summarized. Categories include:
- Immunotherapy including commercial Nivolumab (anti-PD1 agents, anti-PD-L1 agents, anti-CTLA-4 agents and others) by drug name
- Other anti-cancer agents excluding all immunotherapy (approved and investigational) by drug name
- Surgery for treatment of tumors
- Radiotherapy for treatment of tumors
- Any combination of the above

A subject listing of follow-up therapy will also be produced for subjects who had any subsequent therapy.

[figure not shown]

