#### **Surgeries – Imputation Rules.**

If reported surgery date is a full valid date then set start date equal to the date part of surgery date.

In case of partial date, use one of the two imputation rules described below:

A. For data collected on "PRIOR SURGERY RELATED TO CANCER" CRF page:

• If only day is missing then impute as the first day of the month;

- If both day and month are missing then then impute as 01JAN of the year;
- If date is completely missing or invalid then leave missing.
- B. For data collected on other CRF pages (deemed to be on-treatment/subsequent surgeries):
- If only day is missing then
  - If month and year of surgery match month and year of first dose date then impute the missing date as the date of first dose;
  - If month and year of surgery don't match month and year of first dose date then impute as first day of that month and year;
- If both day and month are missing then impute as maximum between 01JAN of the year and date of the first dose;
- If date is completely missing or invalid then leave missing.

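### SAP Appendix 2 back-dates partial radiotherapy and surgery start dates without checking last dose or BICR progression, so a real progression can be censored in primary PFS and a real response left out of BOR.

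*SAP*

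**What the plan says.** SAP Section 10 sends these dates to one place: "Missing and partial radiotherapy and surgery dates will be imputed using algorithm described in APPENDIX 2". Its opening sentence makes the conventions permissive, but Appendix 2 is the only algorithm given for radiotherapy and surgery.

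For a procedure start date with only the day missing there are two branches. In the first-dose month: "If month and year of procedure match month and year of first dose date then impute as date of first dose". In any other month: "then impute as first day of that month and year". With day and month both missing: "If both day and month are missing, then impute as maximum between 01JAN of the year and date of the first dose". A completely missing date stays missing. The surgery rules repeat these steps under branch B: "For data collected on other CRF pages (deemed to be on-treatment/subsequent surgeries").

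The start date feeds two derivations.

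- Primary PFS (SAP 4.1.2): "Subjects who started any subsequent anti-cancer therapy without a prior reported PD per BICR will be censored at the last tumor assessment" on or before the start of that therapy. The definition does not name radiotherapy or surgery. SAP 7.4.3.1 lists "Radiotherapy for treatment of tumors" among the subsequent therapies, and lists surgery in the same way.
- BOR, and so ORR (SAP 4.2.3): responses count only up to progression or "the date of subsequent anti-cancer therapy (including tumor-directed radiotherapy and tumor-directed surgery"), whichever comes first.

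SAP 7.5.2.2 plans a PFS sensitivity analysis that counts events and assessments after subsequent therapy. It also states that the truncated definition remains the basis of the primary test.

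**The concern.** For any therapy given after first dose, Appendix 2 picks the earliest post-dose date that the partial record allows. The SAP checks other imputed dates. An imputed death date is compared with the last known alive date, an imputed progression date with death, and an imputed procedure end date with death or last known alive. The start date, which can truncate a co-primary endpoint, has no such check. A follow-up therapy can thus be dated before the last study dose, or even at the first dose.

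The plan expects progression to come before therapy. Protocol 3.4.3 asks for an evaluation of progression before palliative radiotherapy. Protocol 7.2 and SAP 2.5 ask that, where clinically acceptable, subsequent therapy wait for BICR-assessed progression. If both fall in one month and the day of therapy is missing, the rule can reverse their order. The event then becomes censoring at an earlier scan, and the censoring is tied to the progression itself. For ORR, a response seen before the true start of therapy can be excluded from BOR in the same way.

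**Working it through.** **Inputs from the documents.** Appendix 2 start-date rules. PFS design (SAP Section 5): 250 events per comparison, HR 0.62, two-sided alpha 0.015, 90% power. SAP Appendix 7: power 85%, 80% and 75% at 218, 195 and 175 events; 102 Arm C PD-L1-expressing PFS events by the primary definition against 135 without truncation. One month is 30.4375 days (SAP Section 10).

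**Not given.** The number of partial dates and the gap from progression to therapy. Gaps are assumed below and shown as a range.

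**1. The plan's own power.** Power = Φ(√D/2 × |ln HR| − z), with |ln 0.62| = 0.478 and z = 2.432 for two-sided 0.015. For D = 250: 7.906 × 0.478 − 2.432 = 1.347, so power is 0.911. For 218, 195 and 175 events it is 0.864, 0.817 and 0.767. All are within 2 points of the simulated 90%, 85%, 80% and 75%, so the formula can be used for step 5.

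**2. One subject through the rule (hypothetical dates).** First dose 10 Sep 2018, BICR progression 12 Mar 2019, radiotherapy 25 Mar 2019.

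- Day missing: imputed 1 Mar 2019.
- Day and month missing: imputed 1 Jan 2019.

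Either way the progression now follows the therapy and the subject is censored. Had the therapy fallen in 2018 with only the year known, it would be dated 10 Sep 2018. Every on-study progression or response would then fall after it.

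**3. Day missing, share of true pre-therapy progressions lost per record.** With therapy spread evenly over the month and a gap of g days, progression falls after the first of the therapy month when the therapy day exceeds g + 1. The share is (30.4375 − g − 1)/30.4375. A simulation of the rule agrees.

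| Gap (days) | Formula | Simulated |
|---|---|---|
| 1 | 28.4375/30.4375 = 0.934 | 0.935 |
| 7 | 22.4375/30.4375 = 0.737 | 0.740 |
| 14 | 15.4375/30.4375 = 0.507 | 0.509 |
| 21 | 8.4375/30.4375 = 0.277 | 0.277 |
| 28 | 1.4375/30.4375 = 0.047 | 0.049 |
| 42 | 0 | 0.000 |

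A progression in an earlier calendar month than the therapy is kept.

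**4. Day and month missing.** Simulated with exponential PFS (median about 4 months), earliest progression at day 35 and first doses spread over 900 days. The shares lost are 98%, 96%, 93%, 91% and 87% at gaps of 7, 14, 21, 28 and 42 days. The mean backward shift is 104 to 124 days over gaps of 1 to 42 days.

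Under other conventions, at gaps of 7 and 14 days:

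- 15th of the month (day missing): 28% and 5% lost.
- 1 July (year only): 50% and 48% lost.
- Latest possible date: none lost.

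**5. Effect on power.** Losing 10 of 250 events leaves 240: 7.746 × 0.478 − 2.432 = 1.270, power 0.898 against 0.911. Losing 10 of 195 gives 0.794 against 0.817. Ten lost events need 10/0.51, about 20, day-missing records with a progression 14 days before therapy; about 14 at 7 days (10/0.74); about 36 at 21 days (10/0.28).

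**6. Ceiling.** 135 − 102 = 33 Arm C PD-L1-expressing events (24% of 135) were lost to truncation of every kind at the September 2020 transfer. The imputation part there lies between 0 and 33.

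**The case against.** The case against is substantial, and most of it narrows the point.

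- A reader might infer that events are being lost, or that the 33 in Appendix 7 show it. The documents support neither. They give no count of partial dates. The 33 come from truncation for all causes, including systemic therapy, whose dates follow a separate specification that Appendix 2 does not cover. None is attributed to imputation.
- Only the BOR definition names radiotherapy and surgery. The PFS link is inferred from the wide wording of 4.1.2 and the categories in 7.4.3.1. The SAP also does not say whether the radiotherapy CRF page holds on-treatment records, subsequent records or both.
- The untruncated PFS analysis does not use the imputed date. SAP 7.5.2.1 tabulates censoring for subsequent therapy by arm. These are real safeguards for PFS, but the first changes the question asked and is not the primary test, the second does not show which dates were imputed, and neither covers ORR.
- Waiting for central review makes very short gaps less likely, and at 28 days or more the day-missing loss nearly vanishes. The year-only loss does not.
- Earliest-date imputation has a purpose: it avoids crediting study drug with responses that followed radiotherapy or surgery. Any later convention gives up some of that protection.
- A plain floor at the last dose could override a reported month, because Arms A and B may be dosed beyond progression and dosing may resume after palliative radiotherapy. Letting a same-month progression set the therapy date would let the outcome decide the truncation.

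The last two points shape the remedy. None removes the defect: a stated rule can date follow-up therapy before the last dose, and nothing checks it.

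**Conclusion.** The point holds as a conditional defect. A loss requires a radiotherapy or surgery start date that is partial, and a progression or response after the imputed date but on or before the true start. For PFS it also requires that these modalities count as subsequent anti-cancer therapy.

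Per affected record the loss can be large: 74%, 51% and 28% at assumed gaps of 7, 14 and 21 days with the day missing, and above 85% at every gap tried with only the year known. Across the trial it may be zero. Ten lost events cost about 1 point of power at 250 events and about 2 at 195. The documents do not show that the primary PFS result is materially affected, nor in which direction the hazard ratio would move. The case for changing the SAP is that the rule can produce dates that cannot be right, correction is cheap, and ORR has no fallback analysis.

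**What to change.** 1. For radiotherapy and surgery recorded as follow-up or subsequent therapy, replace the first-dose rule in Appendix 2. Impute no earlier than the last study dose, always within the reported month or year, and not after death or the last known alive date. Leave on-treatment records unchanged.
2. State in SAP 4.1.2 that tumor-directed radiotherapy and surgery truncate PFS as they do BOR.
3. List, by arm, the subjects whose PFS or BOR truncation date is imputed and whose BICR progression or response falls between the earliest and latest possible therapy dates.
4. Add a sensitivity analysis of PFS and ORR using the latest therapy date consistent with the partial record, for both day-missing and year-only dates.

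Item 1 removes dating at first dose but not every reversal. In the worked example, a last dose before 12 March would still leave the imputed start ahead of the progression. Items 3 and 4 show how much that matters.

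The cost is SAP wording and a little programming, best done before database lock. The downside is that later dating may credit an occasional progression or response that truly followed the therapy. If no dates are partial, no result changes.
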